3.7.5 Approach to Missing Data

Clinical trial analyses often are limited to patients with complete data. However, even in cases with low rates of attrition such as our prior VA diabetes RCTs, this strategy may yield overly optimistic effect size estimates. Problems adhering to the protocol or worse health status often are associated with missing data. Although we will conduct an initial analysis using only observed data, we will conduct a second analysis that imputes missing data. We will impute missing data using the method described by Lavori, Dawson, and Sheri.[103] This uses logistic regression to model patients' likelihood of having outcome data and define strata within which outcome values are missing at random. We will then stratify patients according to these propensities and randomly sample from the observed outcome distribution and impute these values for missing data within each stratum. When data are missing for items within scales, we will use recommended imputation procedures rather than deleting patients list-wise from the analysis.[104] In addition, we will compare dropout rates in each arm, using the chi-square tests and compare subjects with complete follow-up to those with missing data with respect to observed baseline characteristics. Finally, we will repeat analyses assuming that all subjects with incomplete data had no improvements in their baseline A1cs as a conservative approach.

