We will follow international guidelines for analysis and reporting of clinical trials.[97] In the first phase (data verification), we will examine the distribution of all study variables to assess extreme values, missing data, variances, possible coding errors, skewness, and type of distribution. We will examine baseline data for clinically important differences across the two study groups for potential prognostic indicators, such as patients' age, race, comorbidities, and baseline use of services. Although we do not anticipate any imbalances due to the randomization, any differences between experimental arms in baseline characteristics will be included as covariates in analyses comparing outcomes. In the second phase of our outcomes analyses, we will evaluate possible bivariate associations between patients' experimental condition and the outcomes, as well as between each covariate and the outcomes, prior to fitting multivariable models. This will be done to determine unadjusted measures of effect, assess possible confounders, and anticipate any collinearity in subsequent analyses. In the final phase we will fit multivariable models to identify main effects.

Analysis Plans by Aim

Aim 1: Test the effectiveness of a technology-enhanced peer coaching (TEC) program in improving glucose control relative to peer support alone. Our past experience in similar patient populations

suggests that the primary endpoint from the trial (change in A1c) will be close to normally distributed. To assess the primary endpoint for Specific Aim 1 (change in mean HbA1c from baseline to 6 months), we will use a general linear mixed regression model:

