where i represents the patient, I represents the intervention, j is the pair-group, β_l are parameters estimated from the data, X_{il} is the value of the l th fixed effect (peer support versus usual care) for the i th patient, β_j are parameters estimated from the data, Z_{ij} is the value of the j th random effect (pairs) for the i th patient, and ϵ_i is the residual error.[99] We anticipate that members of peer coach-peer partner pairs in both arms, because of their interactions with each other, might show a positive intraclass correlation (ICC), a component of the variance attributable to the group. As recommended for group-randomized trials, the mixed model analyses will thus address potentially inflated type I errors that could occur if such clustering were not taken into account.[97] If patients in either arm drop out of the study or request reassignment to another peer coach, they will be analyzed according to their initial pairing in an intent-to-treat analysis.

After unadjusted changes in A1c are determined, further analyses using mixed-model ANCOVA will adjust for confounding effects of any variables that differed substantially between treatment arms. Both unadjusted and adjusted means with 95% confidence intervals will be reported for both arms. While the primary endpoint is the mean difference between baseline and 6-month A1c concentrations, subsequent analyses will be conducted to determine whether the intervention additionally affects the difference between baseline and 12-month A1c (i.e., the sustainability of any treatment effects) using a repeated-measures mixed model ANCOVA.

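### The randomized 6-month A1c comparison needs one named primary analysis that always conditions on baseline A1c and includes every randomized participant

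*SAP*

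**What the plan says.** SAP 3.7, Analysis Plans by Aim, Aim 1, names a regression of this type: "To assess the primary endpoint for Specific Aim 1 (change in mean HbA1c from baseline to 6 months), we will use a general linear mixed". The accompanying definitions index patients and pairs. The random-effect variable "is the value of the j th random effect (pairs) for the i th patient", and there is also a patient-level residual. No time index or within-patient term is defined. The equation itself is not in the text available for review, so the reading that each patient contributes one change score is an inference from these definitions.

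The same section separates two questions: "While the primary endpoint is the mean difference between baseline and 6-month A1c concentrations", and a later comparison of baseline with "12-month A1c (i.e., the sustainability of any treatment effects) using a repeated-measures mixed model ANCOVA". The repeated-measures model is named only for the second.

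On covariates, Approach to All Analyses and Aim 1 adjust the randomized comparison for characteristics found to differ between arms. Baseline A1c is a fixed covariate only for the comparison with the observational usual-care group.

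On missing outcomes, SAP 3.7.5 warns about analyses limited to complete data: "this strategy may yield overly optimistic effect size estimates". It then sets out three analyses: "Although we will conduct an initial analysis using only observed data, we will conduct a second analysis that imputes missing data", and finally a repeat in which patients with incomplete data are taken to have had no improvement. The imputation samples observed outcomes within strata of the propensity to have outcome data.

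**The concern.** A patient without a 6-month A1c has no change score. If the model holds one change score per patient, that patient's baseline and any 12-month value are unused in the observed-data analysis. The usual defence, that a likelihood-based mixed model is valid when data are missing at random, requires the patient's other measurements to be in the model. A random effect for pairs does not put them there.

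Change in A1c is normally related to its starting value. If one arm loses more patients with high baseline values than the other, the remaining patients differ at baseline and the change-score contrast absorbs part of that difference. The plan adjusts for baseline A1c only when an imbalance is noticed, and it does not say how large an imbalance counts or whether it is judged among all randomized patients or only those analyzed.

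Since no analysis is named as primary, three results for the main endpoint could also be available with no stated rule for which one decides the trial.

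**Working it through.** **The plan's own figure.** Inputs from SAP 3.7, Unit of Analysis and Sample Size Calculation: difference 0.5, SD of change 1.45, two-sided alpha 0.05, power 80%, intraclass correlation 0.03, 148 patients and 37 mentors per arm after attrition, 15% attrition, 174 recruited per arm.

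- Unclustered size per arm: 2 × [1.45 × (1.960 + 0.842) / 0.5]², which gives 133 after rounding up.
- Design effect with 148/37 = 4 patients per mentor: 1 + 3 × 0.03 = 1.09, so 133 × 1.09 = 145. Counting the mentor as a fifth member: 1.12, so 133 × 1.12 = 149. The stated 148 is reproduced within rounding.
- Attrition: 148 / 0.85 = 174.1, against 174 stated.
- Absent from the observed-data analysis: 0.15 × 174 = 26 per arm, 52 of 348 in all.

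The sample size is not in question.

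**Bias of the change score.** The documents do not give the following, so they are assumed: baseline SD 1.6, the same SD at 6 months, correlation 0.59, no true effect, about 16% missing, and drop-out log-odds of 0.6 per SD of baseline A1c.

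- Check on the assumptions: SD of change = 1.6 × √(2 × 0.41) = 1.45, the plan's value.
- Slope of change on baseline: 0.59 − 1 = −0.41.
- For logistic drop-out with a normal baseline, the completers' mean shifts by −0.6 × E[p(1−p)] / (1 − E[p]) SDs, where p is the drop-out probability. With E[p] = 0.16, numerical integration gives E[p(1−p)] = 0.128, so the shift is −0.6 × 0.128 / 0.84 = −0.091 SD, or −0.146 A1c points.
- Dependence in one arm only: −0.41 × −0.146 = 0.06 points, 12% of the 0.5 target.
- Opposite directions: 2 × 0.06 = 0.12 points, 24% of the target.
- Same dependence and same rate in both arms: the shifts cancel and the bias is 0.

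The sign depends on which arm loses its high-baseline patients.

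**Sensitivity to the baseline SD.** Holding the SD of change at 1.45, the one-arm bias is 0.091 × 1.45² / (2 × baseline SD): 0.07 at a baseline SD of 1.3, 0.06 at 1.6 and 0.05 at 2.0.

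**Simulation of the same setting** (174 per arm, 2,000 trials):

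| Analysis | Bias, one arm | Bias, opposite directions |
|---|---|---|
| Observed change score | 0.063 | 0.127 |
| ANCOVA on baseline, same observed patients | 0.002 | 0.005 |
| Propensity-stratum imputation (strata assumed within arm and driven by baseline A1c) | 0.011 | 0.017 |
| No-improvement analysis | 0.053 | 0.106 |

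With the same dependence in both arms, the change-score bias was 0.003. Milder contrasts gave 0.033 (log-odds 0 versus 0.3) and 0.029 (0.3 versus 0.6).

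**Precision.** With equal SDs, conditioning on baseline multiplies the standard error by √((1 + 0.59)/2) = 0.89. The simulation gave 0.151 to 0.154 against 0.169, about 10% lower. This gain does not need differential drop-out.

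**The case against.** A reader might infer that the primary analysis is complete-case. The documents do not say so: the observed-data analysis is called initial, not primary. Powering on patients left after attrition does not settle the matter, because trials inflate for attrition under any missing-data method.

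A reader might also infer that the plan breaks its intent-to-treat commitment. That sentence says of patients who drop out or ask for another coach that "they will be analyzed according to their initial pairing in an intent-to-treat analysis". It concerns which pairing they are counted under. Patients who leave the program but have a 6-month A1c stay in, and the sentence does not promise that patients without an outcome enter every analysis.

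Nor does the plan ignore missing data. Its warning about complete-case results is its reason for adding imputation. The imputation and no-improvement analyses cover all randomized patients, and drop-out is compared by arm. In the simulation, the imputation removed most of the bias.

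Finally, it is tempting to credit any improvement to restoring the excluded patients. ANCOVA on the same observed patients removes the bias and gives the precision gain, so the demonstrated benefit comes from conditioning on baseline A1c. Any further gain from 12-month values was not measured.

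All of this stands. It is also true that the documents give no reason to expect differential drop-out, that both arms receive peer coaching, and that the SAP describes 15% attrition as above any of its earlier VA diabetes trials. What remains is that no analysis is named as primary, and baseline A1c is not guaranteed a place in the randomized comparison. The definitions allow several fixed effects, so a baseline term in the missing equation cannot be excluded, but the text does not state one.

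**Conclusion.** The concern holds in limited form. The SAP leaves open which of three 6-month analyses decides the trial, makes adjustment for baseline A1c conditional on an observed imbalance, and reserves the repeated-measures model for 12 months. About 26 of 174 patients per arm would be absent from the observed-data analysis if attrition reaches 15%.

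The bias of 0.06 to 0.12 A1c points is illustrative. It requires drop-out to depend on baseline A1c differently by arm, and the upper figure requires opposite directions. The size of the precision gain rests on the assumed correlation, but that gain is available under any drop-out pattern. The plan should be changed, though nothing here shows that its result would be invalid.

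**What to change.** State in SAP 3.7 (Aim 1) and 3.7.5 that one 6-month analysis is primary, that it always conditions on baseline A1c, and that it includes all randomized participants. One suitable choice is to extend the planned repeated-measures mixed model to baseline, 6- and 12-month A1c, with a common baseline mean across arms, arm-by-visit terms, an unstructured within-patient covariance and a random mentor intercept. The 6-month arm contrast would be primary and the 12-month contrast would address sustainability. A mixed-model ANCOVA with baseline A1c always included, combined with multiple imputation, would also meet the need.

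Keep the observed-data change score, the propensity-stratum imputation and the no-improvement analysis, and label them as sensitivity analyses.

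The cost is SAP wording and a slightly more complex model. No new data are needed: the Protocol (Measures and Data Collection, Overview) already schedules A1c at all three visits.

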3.7 Analyses

Unit of Analysis and Sample Size Calculation

Patients within pairs (peer-peer coach dyads) will be the primary unit of analysis for the study. Thus, we calculated the sample size to adjust for the likely correlation between members of the pairs (intraclass correlation, or rho) in the intervention group. Accordingly, we calculated the sample size to provide 80% power to detect a difference between experimental groups of 0.5% in A1c with an alpha of .05, two-tailed.[95] We conducted the power analysis using the methods of Cohen and, based on the within-pair ICC of our prior reciprocal peer support intervention, adjusted for a within-pair intraclass correlation of 0.03 as implemented in STATA 12 software.[96] We estimated the standard deviation of a decline in A1c in this population (1.45) using data from our prior randomized controlled trials.[9,40] To provide the needed power, 148 subjects will be needed in each group (after attrition) and 74 peer mentors (clusters) across both groups (37 in each group). To conservatively allow for up to 15% attrition, a rate higher than occurred in any of our prior VA diabetes RCTs, we will recruit 174 patients for each arm, for a total of 348 patients, and a total number of 87 peer mentors. The estimate of the standard error of the change in BP was estimated from a database of actual BPs obtained in routine clinical practice for 24,000 patients with diabetes and hypertension in one large service network in the VA over a 24-month period in FY 2004-2005. It depends on both the variation in BP change at the person level and variability within person between measurements. We estimated the standard error for the change in blood pressure as 17 mmHg. Our target sample size will provide 90% power to detect a difference between experimental groups of 5 mmHg and differences between each of our key patient-centered outcome measures.

Approach to All Analyses

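### Minor: the chi-square test of dropout by arm treats patients who share a mentor as independent, so its type I error will exceed 5% if dropout is positively correlated within mentor

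*SAP*

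**What the plan says.** SAP section 3.7.5 (Approach to Missing Data) lists several checks, among them: "we will compare dropout rates in each arm, using the chi-square tests". It mentions no adjustment for mentor, no continuity correction and no significance level for this test.

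Elsewhere the SAP treats mentors as clusters. The sample-size paragraph of section 3.7 counts "74 peer mentors (clusters) across both groups (37 in each group" and states that the calculation was "adjusted for a within-pair intraclass correlation of 0.03". The Aim 1 analysis plan gives the reason for a mixed model with a random effect for pairs: it addresses "potentially inflated type I errors that could occur if such clustering were not taken into account". The Aim 2 plan carries the same approach to the other outcomes, with mixed models for continuous measures and GEE for ordinal ones. The Aim 1 plan also keeps patients who drop out or change coach in their initial pairing.

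**The concern.** The dropout comparison is a between-arm comparison of the same patients, under the same mentors, as the outcome analyses. An ordinary chi-square takes its variance from independent patients. If patients with the same mentor tend to stay or leave together, that variance is too small and the test rejects too often when the arms do not differ.

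Some correlation is plausible in this trial. Section 3.7.5 links missing data to problems in following the protocol. The protocol's Overview of measures expects some mentors to keep regular contact and others not to, and the Aim 3 plan measures engagement by dyad. A few inactive mentors falling by chance in one arm could then look like an effect of the programme on dropout.

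What is at stake is limited. This is the only formal test of differential loss between arms that the plan states, and a false signal from it could cast unwarranted doubt on the A1c comparison.

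**Working it through.** **Inputs from SAP section 3.7 (sample-size paragraph)**
- Target: "we calculated the sample size to provide 80% power to detect a difference between experimental groups", namely "0.5% in A1c with an alpha of .05, two-tailed".
- SD of A1c change: 1.45.
- ICC for A1c: 0.03.
- Patients and mentors: 148 per arm with 37 mentors after attrition; 174 per arm (348 in total) with 87 mentors recruited.
- Attrition: up to 15%.

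**Assumptions.** The dropout test is two-sided at 0.05, clusters are of equal size, each mentor belongs to one arm, and the dropout ICC is unknown.

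**Step 1: cluster size.** 148/37 = 4 and 348/87 = 4 patients per mentor.

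**Step 2: reproduce the plan's sample size.**
- Unclustered, normal approximation: n = 2 × [1.45 × (1.960 + 0.842)/0.5]² = 132.0 per arm. With the t distribution it is 132.99.
- Design effect: 1 + (4 − 1) × 0.03 = 1.09.
- 132.99 × 1.09 = 144.95, and 144.95/4 = 36.2. That needs 37 mentors, and 37 × 4 = 148 per arm, as stated.
- 148/0.85 = 174.1, matching the stated 174.

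A cluster of five under the normal approximation also reaches 148 (132.02 × 1.12 = 147.9), so this does not prove which route the plan took. The figure of four patients per mentor does not depend on it, because it follows directly from step 1.

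**Step 3: type I error of an unadjusted chi-square.** With design effect DE = 1 + 3 × ICC, the true two-sided error at nominal 5% is 2 × [1 − Φ(1.96/√DE)].

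| Dropout ICC | DE | True type I error | Status of the ICC |
|---|---|---|---|
| 0 | 1.00 | 5.0% | no clustering |
| 0.01 | 1.03 | 5.3% | assumed |
| 0.03 | 1.09 | 6.0% | plan's A1c value, borrowed |
| 0.05 | 1.15 | 6.8% | assumed |
| 0.10 | 1.30 | 8.6% | assumed |

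**Step 4: check without the normal approximation.** An exact beta-binomial calculation used 44 and 43 mentors of four patients, with 15% dropout in both arms. The Pearson chi-square gives 4.9% at ICC 0, 5.3% at 0.01, 6.0% at 0.03, 6.7% at 0.05 and 8.5% at 0.10, in agreement with step 3.

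**Step 5: effect of a continuity correction.** In the same exact calculation, a Yates-corrected test gives 3.5% at ICC 0, 4.4% at 0.03, 5.0% at 0.05 and 6.5% at 0.10.

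**Step 6: what adjustment does to the interval.** With 15% dropout in each arm of 174, the unadjusted standard error of the difference is √(2 × 0.15 × 0.85/174) = 0.0383. The 95% half-width is 1.96 × 0.0383 = 7.5 percentage points. Multiplying by √1.09 = 1.044 gives 7.8 points at ICC 0.03, and by √1.30 = 1.140 gives 8.6 points at ICC 0.10.

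**The case against.** The strongest case is that this is immaterial, and much of it stands.

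- **No ICC for dropout.** A reader might infer that the plan's own reasoning shows the dropout test's error is too high. It does not. The Aim 1 text is conditional, concerns A1c, and gives interaction between pair members as the source of the correlation. Inflation for dropout is plausible but not established.
- **Small size.** The only figure with a basis in the documents is about one percentage point, and it borrows the A1c ICC. With a continuity correction the error stays below 5% at that ICC. However, the SAP specifies no such correction. It also does not model the clustering: the corrected test still rises from 3.5% to 4.4% between ICC 0 and 0.03.
- **Uncertain mechanism.** Patients may ask for another coach. A1c is measured by trained staff, and each completed assessment is paid at $25 (protocol, Overview and section 3.6.2). A poor mentor therefore need not mean a missing outcome. This is a reason to start the range at ICC 0.
- **No decision depends on the test.** The observed-data analysis, the imputation, the comparison of completers with non-completers and the no-improvement analysis are all run whatever the chi-square shows. A reader might infer that trust in the A1c result turns on this test; the documents attach no such role to it.
- **The error is on the cautious side.** An unadjusted test flags differential loss slightly too often. If mentors with many dropouts fall by chance in one arm, the missing data are still unbalanced, and an adjusted test is less likely to flag that. This is a real cost, met by reporting the observed rates whatever the p-value.

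These points lower the importance. They do not make an independence-based test right for a design with four patients per mentor, and an unknown ICC favours a method that allows for correlation over one that fixes it at zero.

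**Conclusion.** The point holds as a minor inconsistency. The dropout comparison ignores the shared mentor, unlike the outcome models. Its type I error will exceed 5% if dropout is positively correlated within mentor, and will not if there is no such correlation. Over ICCs from 0 to 0.10 the error runs from 5.0% to 8.6%. The 6.0% figure borrows the A1c ICC, and 8.6% rests on an assumed one, so neither should be read as the plan's own figure for dropout.

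The result assumes a two-sided 5% test without continuity correction, equal clusters of four and mentors nested in arm. A reader might infer that the A1c analysis is compromised. It is not: the primary test, its alpha and the sample size do not use this comparison.

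**What to change.** In SAP section 3.7.5, replace the chi-square with a logistic GEE or mixed logistic model for dropout on arm, clustered on the initially assigned mentor. A design-effect-adjusted chi-square would also serve, with the dropout ICC estimated from the trial's own data. Report the observed dropout rates by arm and their difference with a cluster-adjusted 95% CI.

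At 15% attrition there would be about 348 × 0.15 = 52 dropouts over 87 mentors, or 0.6 per mentor. A random-effect variance may be poorly estimated from so few events, so GEE or the adjusted chi-square is the simpler choice.

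The change takes about one line. GEE is already planned for Aim 2, and the Aim 1 plan already keeps patients in their initial pairing, so the cluster variable exists. The cost is a slightly wider interval (a half-width of about 7.8 rather than 7.5 points at ICC 0.03) and a slightly less sensitive warning check. The SAP should therefore say that the observed imbalance will be reported and discussed whatever the p-value.
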